### 1.1 Background

Effective communication around serious illness is an essential clinical competency for all physicians. Physicians, however, often fail to disclose prognostic information and to adequately solicit patient values. Cited barriers to effective communication include insufficient physician training in communication and difficulty in dealing with patient emotion.

While formal communication skills training programs improve learners' behaviors in proximate, controlled settings (e.g., simulation), the evidence that this training has long-term impacts on learners' behavior and associated patient outcomes is limited and mostly demonstrates null effects. Human behavior can be resistant to change, and psychologic theory suggests twelve domains for why physician behavior does not change. One of these twelve domains is emotion regulation. Emotion regulation, defined as the ability to respond to ongoing demands of experience with a sufficiently flexible range of emotions, is necessary for effective prognostic disclosure, given both patient and provider have emotional reactions to such information. Burnout, a process involving emotional exhaustion, depersonalization, and low personal accomplishment, adversely impacts emotion regulation. No studies have addressed the potential role of emotion regulation and burnout as physician factors affecting the acquisition of physician communication skills.

The purpose of this study is to twofold. First, evaluate the efficacy of a communication skill training we integrated into graduate medical education by longitudinally tracking participants' documentation behavior. Second, perform exploratory analyses of physicians' emotion regulation skills and burnout as potential mechanisms for communication skill acquisition.

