**Skills acquisition checklist** - used by independent observer during simulated patient encounters to evaluate trainees. One point is assigned for each item used by the trainee. The checklist contains three scores: conversation guide specific items (16 points), global communication skills (9 points), and a combined score (25 points). This checklist was developed internally and based on the experience training residents in the Serious Illness Conversation Guide (SICG).

**Template Use** –The analytics team at our institution is able to link the smartform to the physician who made alterations, the content of those alterations, patient and date of change.

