### **Aim 2. Test the relationship between emotion regulation and burnout on trainee skill enactment over 12 months.**

Hypothesis: Trainees in the top half of template users will have higher a TOTAL emotion-regulation score than trainees in the bottom half (Ha2a). Trainees in the top half of template users will have lower Emotional Exhaustion scores than trainees in the bottom half (Ha2b).

Rationale: Given their high emotional content, a physician's ability to regulate their own emotions and emotional exhaustion may impact their capacity to engage in serious illness conversations. In a healthcare setting, the ESRQ was used to assess non-physician participants' competence to cope with specific and general aspects of negative emotions. We know of no studies examining its role in physicians and specifically medical trainees.

[figure not shown]
Outcomes: For ERSQ and MBI achieve complete data collection in ≥80% of willing participants (primary).

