## 3 Study Design

### **3.1 General Design**

This is a single-institution cohort study with two tiers. Tier 1 is an education study where participants can complete electronic surveys on their pre and post intervention confidence, perform two simulated patient encounters and have their documentation of electronic template monitored longitudinally over 12 months. Participants are free to opt out of any activity related to education assessment or system-based interventions to promote the use of learned skills (e.g. priming or profile feedback). Signed informed consent will Not be required for this tier.

Tier 2 is a behavioral study where participants, in addition to all of Tier 1 activities, also complete psychological inventories at three time points to measure emotion regulation and burnout, and participate in a semi-structured interview. We will require signed informed consent to participate in Tier 2.

**Figure 1** Study Design

Participant duration – each participant will be followed for 12 months beginning with their first communication training

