### **5.1 Before Communication Training Activities**

Tier 1 (education-only subjects): Three to four weeks prior to the subject's two-week palliative care elective they will be sent an email to complete an online confidence survey. They will receive email reminders to complete the survey until survey is completed.

Tier 2 (education + behavioral subjects): Subjects will have reviewed and signed consent documentation. In addition to the above online confidence survey, they will also receive email to complete electronic ERSQ and MBI.

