### **6 Statistical Plan**

#### **6.1 Sample Size Justification**

Primary Hypothesis: Template use for both trainee subgroups will increase from zero after training for  $\geq 50\%$  of trainee (Ha1a)

Let null hypothesis Hnull1a be  $p < 50\%$  and alternative hypothesis be Ha1a be  $p = p_1 \geq 50\%$ , where p is proportion of trainees who have any documented template use. Sample size of 42 (12 fellows and 30 eligible residents who have completed the education intervention by the end of the grant award period [June 2020]) enables us to have Minimum Detectable Difference (MDD) 19.05%, i.e., the least p1 is 69.05%, with 80% of power and 2.5% significance level using one-side proportion test with exact test.

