#### **6.2 Analysis Plan**

Primary Hypothesis: Ha1a

We will calculate the proportion of trainees with template use and provide 95% confidence intervals with exact method, then we will test the hypothesis using a proportion test.

Secondary Hypotheses

Ha1b: Trainee and faculty confidence will increase after training for  $\geq 50\%$  of participants.

We define increased confidence as trainee and faculty post-intervention confidence scores of 4 or 5 on a 5-point Likert scale. We will calculate proportion of subjects who have increased confidence and show 95% confidence intervals as well, then we will use a proportion test for the hypothesis.

**Ha1c: Observed communication skills scores at the second and third simulated patient encounter will improve over the first encounter.**

The observed communication skills scores have three different scores (two sub-scores and one combined/total score). We will apply a linear mixed model with random subject effect to test whether each of three scores are different from encounter 1 to 2 and 3 separately. P-values will be adjusted for multiple tests by the Dunnett method.

**Ha2a: Trainees in the top half of template users will have higher total emotion-regulation competences (TOTAL) than trainees in the bottom.**

The ERSQ yields 10 different scales of emotion regulation: 9 specific competences and 1 TOTAL competency which is the average of the nine scales. We will provide summary statistics (mean and standard deviation) of TOTAL competency and use a two-sample t-test to test differences between the top half and low half groups of patients. P-value will be presented.

**Ha2b: Trainees in the top half of template users will have lower Emotional Exhaustion (EE) scores than trainees in the bottom half.**

We will provide summary statistics (mean and standard deviation) of EE scores and use a two-sample t-test to test differences between the top half and low half groups of patients. P-value will be presented

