### **6.3 Subject Population(s) for Analysis**

*Primary outcome is all residents and fellows trained. Secondary outcomes evaluating emotion regulation skill and burnout are in all residents and fellows who consented to be part of Tier 2 – the behavioral study part.*

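### Ha2a and Ha2b split template use into halves and compare scores by unadjusted t-test; a partial Spearman correlation adjusted for trainee type uses the same data with more power

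*Combined protocol and SAP*

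**What the plan says.** Section 2 (Aim 2) states two directional hypotheses. Ha2a is "Trainees in the top half of template users will have higher a TOTAL emotion-regulation score than trainees in the bottom half". Ha2b predicts the reverse direction for the MBI Emotional Exhaustion (EE) score. Section 6.2 handles both the same way: report mean and SD, "use a two-sample t-test to test differences between the top half and low half groups of patients", and present the p-value. It names no covariate, no rule for ties at the cut and no sensitivity analysis.

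On the population, section 6.3 says: "Secondary outcomes evaluating emotion regulation skill and burnout are in all residents and fellows who consented to be part of Tier 2". Section 6.1 counts 42 trainees (12 fellows, 30 residents), so Tier 2 has at most 42. Its size is not stated.

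On timing, section 3.1 says Tier 2 participants "also complete psychological inventories at three time points to measure emotion regulation and burnout". The first is before training (section 5.1: "they will also receive email to complete electronic ERSQ and MBI") and the others are at 6 and 12 months (section 5.6). Section 6.2 does not say which one is tested.

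On template use, section 1.2 says the analytics team can "link the smartform to the physician who made alterations, the content of those alterations, patient and date of change", so a count per trainee can be built. Section 1.1 gives the status of Aim 2: "Second, perform exploratory analyses of physicians".

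**The concern.** Aim 2 asks whether emotion regulation and burnout relate to how much trainees use what they were taught. The planned test is weak for that question in three ways.

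1. **Lost information.** A trainee just above the middle is treated like the heaviest user. With at most 42 trainees there is little information to spare.
2. **Undefined groups.** Use is a count that starts at zero, so several trainees may share the value at the cut. Without a tie rule, who falls in which half is arbitrary and the p-value can depend on it.
3. **Trainee type.** Residents and fellows are pooled. If they differ in both use and score, the t-test can show a difference with no relation inside either group, or hide one that exists. The documents do not say whether they differ.

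At stake is the chance of seeing a real relation and the reading of the two p-values.

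**Working it through.** The plan gives no power, significance level or sidedness for Ha2a and Ha2b, so there is no figure to reproduce. A two-sided 5% level is assumed throughout.

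**Inputs from the documents.** N is at most 42, with 12 fellows and 30 residents (section 6.1). The primary hypothesis concerns any use (section 6.1: "where p is proportion of trainees who have any documented template use"), with 50% as the null and 69.05% as the planned alternative. Those values suggest zero shares of 1 - 0.50 = 0.50 and 1 - 0.6905 = 0.31, although they describe all 42 trainees and not Tier 2.

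**Assumptions.** Tier 2 size of 28 (8 fellows, 20 residents) as a second case; negative-binomial counts with dispersion 0.35 to 2.0; zero shares of 10% to 50%; a Gaussian-copula link between score and count with latent correlation r. Settings had 8,000 to 10,000 simulated datasets unless stated.

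**The two tests.**
- Split: order trainees by count, break ties at random, pooled two-sample t-test.
- Partial Spearman: mid-rank count and score, take residuals of each on resident/fellow status, correlate the residuals to get r_p, and refer t = r_p × √((n - 3)/(1 - r_p²)) to t with n - 3 df.

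**Large-sample efficiency.** Against the full correlation under bivariate normality, an even split has efficiency 2/π = 0.64 and Spearman 9/π² = 0.91. The ratio is 0.64/0.91 = 0.70, so 42 trainees analysed by halves are worth about 0.70 × 42 = 29 analysed by ranks. With 21 per half, the standardised difference detectable with 80% power is (1.96 + 0.84) × √(2/21) = 0.86.

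**Simulated results.**

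| Quantity | n | Split t-test | Partial Spearman |
|---|---|---|---|
| Power at r = 0.4 | 42 | 49-56% | 61-70% |
| Power at r = 0.4 | 28 | 33-38% | 43-51% |
| Power at r = 0.3 | 42 | 30-33% | 37-44% |
| Power at r = 0.5 | 42 | 69-78% | 82-89% |
| r detectable with 80% power | 42 | 0.52-0.55 | 0.46-0.48 |
| r detectable with 80% power | 28 | 0.62-0.68 | 0.55-0.58 |
| Trainees for 80% power at r = 0.4 | - | 76-81 | 56-63 |

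At r = 0 both tests reject in about 5%. The detectable r and the trainee numbers use dispersion 0.7 and 5,000 datasets per grid point.

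**A different count model** (3,000 datasets, n = 42, r = 0.4) gives 51% versus 66% with 69% users, 48% versus 62% with 50% users, and 39% versus 56% with 40% users. With continuous use it gives 57% (split), 56% (split, adjusted), 72% (Spearman) and 71% (partial Spearman). The gain therefore comes from not splitting; adjustment costs about one point.

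**Ties.** The cut falls on a tie in 39-93% of datasets at n = 42 and 29-89% at n = 28. With r = 0.4, 31-50% zeros and 200 random tie-breaks for each of 2,000 datasets, at least one tie-break changes the p < 0.05 result in 18-67% of datasets at n = 42 and 14-59% at n = 28. On a stricter count, where 10-90% of tie-breaks are significant, it is 17-48% at n = 42. Zeros themselves straddle the cut only if fewer than half use the template. The exact binomial P(X < 21) for n = 42 is 0.439, 0.071 and 0.003 at p = 0.50, 0.60 and 0.6905. For n = 28, P(X < 14) is 0.43, 0.10 and 0.011.

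**Confounding.** With no relation inside either group, the split t-test at n = 42 rejects in:
- 5% if only use differs by trainee type;
- 6-8% if use differs by 0.5-1.0 SD and score by 0.5 SD;
- 22-23% if use differs by 1.5 SD and score by 1.0 SD.

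At n = 28 the moderate and large cases give 5-7% and 15-17%. The adjusted test stays near 5%. Masking also occurs: in the second count model, with fellows 1 SD higher on use, 0.5 SD lower on score, and r = 0.4, power is 25% for the split against 66%.

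**The case against.** The strongest reply is that little hangs on these tests. Section 1.1 calls the work exploratory, Aim 2's own primary outcome in section 2 is completeness of the inventories, and section 6.2 attaches no decision to the p-values. This limits the importance of the point. It does not remove it, because both hypotheses are directional and will be reported with p-values.

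Second, the replacement does not make the aim well powered: even partial Spearman needs 56-63 trainees for 80% power at r = 0.4. That stands. The change is a better use of a small sample, not a rescue.

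Third, the advantage assumes a monotone relation. If scores truly step by 0.8 SD between the halves, which favours the split, power is 56-59% versus 54-60% at n = 42 and 38-40% versus 37-43% at n = 28. The gain then largely disappears, but at most about 2 points are lost.

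Fourth, confounding is hypothetical and the large case is extreme. That is fair: at moderate differences the inflation is small. When both shifts run the same way and a relation exists, the t-test can even reject more often, but part of that is confounding.

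Fifth, a one-line tie rule would settle the allocation. It would, but it would not recover the lost information.

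Finally, the count has its own gaps. Section 1.3 describes a dotphrase form as well as the smartform, section 4.4.2 follows leavers only to their last working day, and the half of users named in Aim 2 might exclude non-users. These affect the planned halves just as much.

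**Conclusion.** The concern holds, as an improvement to consider. The planned analysis keeps its 5% size when trainee type is not a confounder, so it is not invalid. It is inefficient, its groups are undefined when ties occur at the cut, and it is open to confounding by trainee type. At r = 0.4 the gain from the replacement is about 10 to 14 power points under negative-binomial counts.

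The direction of the efficiency loss for a monotone relation is firm. The magnitudes rest on the assumed correlation, count distribution, zero share, Tier 2 size and trainee-type differences, none of which the documents give. The primary endpoint is unaffected.

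**What to change.** - For each hypothesis, make the test a partial Spearman correlation, adjusted for resident/fellow status, between the 12-month template count and the pre-training score: ERSQ TOTAL for Ha2a, EE for Ha2b. Include all Tier 2 trainees, with zeros; this also settles who is being ranked. The pre-training score precedes the use it is meant to explain.
- Reword the hypotheses: higher TOTAL, or lower EE, goes with more template use.
- Keep the half-split means and SDs, and the 6- and 12-month scores, as description, with a stated tie rule for the halves.

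The cost is new wording in section 2 (Aim 2), section 6.2 and the t-test entry in the Study Summary, plus a few lines of code. No new data are needed: use is already linked to the physician and the pre-training inventories are already planned. The result becomes a rank correlation instead of a mean difference, and one degree of freedom goes to trainee type.

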### **6.3 Subject Population(s) for Analysis**

*Primary outcome is all residents and fellows trained. Secondary outcomes evaluating emotion regulation skill and burnout are in all residents and fellows who consented to be part of Tier 2 – the behavioral study part.*

## **7 Investigator reporting: notifying the Dartmouth IRB**

### **7.1 Definitions**

This section describes the requirements for safety reporting by investigators who are Dartmouth faculty, affiliated with a Dartmouth research site, or otherwise responsible for safety reporting to the Dartmouth IRB. The Dartmouth IRB requires reporting of those events related to study participation that are unforeseen and indicate that participants or others are at increased risk of harm. The Dartmouth IRB requires researchers to submit reports of *any incident, experience, or outcome that meets each of the following criteria:*

- **Unanticipated** in terms of nature, severity, or frequency given: (a) the research procedures that are described in the protocol-related documents, such as the IRB-approved research protocol and consent document; and (b) the characteristics of the subject population being studied; and
- **Possibly related** to participation in the research means there is a reasonable possibility that the incident, experience, or outcome may have been associated with research participation; and
- **The problem suggests that the research places subjects or others at a greater risk of harm** (including physical, psychological, emotional, economic, legal, or social harms) than was previously known or recognized.

### **7.2 Reporting Process**

Unanticipated problems posing risks to subjects or others as noted above will be reported to the Dartmouth IRB using the form: “Unanticipated Problem Involving Risks to Subjects or Others (UPR).”

Copies of each report and documentation of IRB notification and receipt will be kept in the Clinical Investigator's study file.

### **7.2 *Other Reportable events:***

For behavioral trials, the following events are also reportable to the Dartmouth IRB:

- Breach of confidentiality
- Change to the protocol taken without prior IRB review to eliminate apparent immediate hazard to a research participant.
- Complaint of a participant when the complaint indicates unexpected risks or the complaint cannot be resolved by the research team.
- Protocol deviation (meaning an accidental or unintentional deviation from the IRB approved protocol) that in the opinion of the investigator placed one or more participants at increased risk, or affects the rights or welfare of subjects.

## **8 Data Handling and Record Keeping**

### **8.1 *Confidentiality***

Information about study subjects will be kept confidential. Presentations of any results of the data that results from this study will be de-identified. Results that could be linked to an individual will be aggregated or omitted in publication or presentations.

In the event that a subject revokes authorization to collect or use their data, the investigator, by regulation, retains the ability to use all information collected prior to the revocation of subject authorization.

### **8.2 *Source Documents***

Source data is all information, original records of surveys, observations, interviews, or other activities in a study necessary for the reconstruction and evaluation of the study. Source data are contained in source documents. Examples of these original documents, and data records include: electronic survey results, psychologic inventory results (e.g. ERSQ and MBI), simulated patient encounter assessments, recorded semi-structured interviews, patient lists with subjects responses to priming questions, and documentation of template in the electronic medical record.

### **8.3 *Records Retention***

We plan to retain record of study subject for one year following the study completion of the last study participant enrolled (an additional 12 months after the subject's initial 12 month assessment following training completion). This will allow for additional data analysis as the investigators plan to publish the results of the study.

## **9 Study Monitoring**

This study will be monitored according to the monitoring plan outlined IRB research plan, entitle Study Progress Monitoring. The investigator will allocate adequate time for such monitoring activities.

## **10 Ethical Considerations**

This study is to be conducted according to US and international standards of Good Clinical Practice (FDA Title 21 part 312 and International Conference on Harmonization guidelines), applicable government regulations and Institutional research policies and procedures.

This protocol and any amendments will be submitted to a properly constituted independent Ethics Committee (EC) or Institutional Review Board (IRB), in agreement with local legal prescriptions, for formal approval of the study conduct. The decision of the EC/IRB concerning the conduct of the study will be made in writing to the investigator and a copy of this decision will be provided to the sponsor before commencement of this study. The investigator should provide a list of EC/IRB members and their affiliate to the sponsor.

For this study, participants in Tier 2 (behavioral research) will be provided a consent form describing this study and providing sufficient information for subjects to make an informed decision about their participation in this study. See Attachment for a copy of the Subject Informed Consent Form. This consent form will be submitted with the protocol for review and approval by the EC/IRB for the study. The formal consent of a subject, using the EC/IRB-approved consent form, must be obtained before that subject undergoes any study procedure. The consent form must be signed by the subject or legally acceptable surrogate, and the investigator-designated research professional obtaining the consent.

## **11 Study Finances**

### ***11.1 Funding Source***

Funding from the Dartmouth-Hitchcock Medical Center Department of Internal Medicine section of Hematology-Oncology. A grant application to the American Society of Clinical Oncology for this project was submitted and its status is pending.

### ***11.2 Conflict of Interest***

Any investigator who has a conflict of interest with this study (patent ownership, royalties, or financial gain greater than the minimum allowable by their institution, etc.) must have the conflict reviewed by a properly constituted Conflict of Interest Committee with a Committee-sanctioned conflict management plan that has been reviewed and approved by the study sponsor prior to participation in this study. All Dartmouth-Hitchcock investigators will follow the Dartmouth-Hitchcock conflict of interest policy.

